2.2 Secondary Objectives

The secondary objectives of this study are to assess the late toxicities, cosmesis, and clinical efficacy of accelerated partial breast radiation using protons.

3 Subject Selection and Withdrawal

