7.1.3 Endpoints

Primary Endpoints

Feasibility will be based on multiple radiation planning and treatment parameters. Should a patient experience one of the following events, treatment will be deemed infeasible:

- a) Patient cannot be given treatment because anatomy is such that a dosimetrically satisfactory treatment plan cannot be devised. For example, the dosimetry is unsatisfactory if < 95% of the target volume is covered by 95% of the dose.
- b) Patient is unable to tolerate more than 20% of treatments using proton radiotherapy (i.e., >2 of the 10 fractions). This can be for any reason, including the inability to set the patient up within acceptable limits of tolerance, or the patient is unable to tolerate treatment position or immobilization for duration of treatment. Thus, up to 20% (i.e., 2 of the 10 fractions) of treatments could be delivered using photons.
- c) Patient is unable to complete all treatment within 5 days of the estimated date of treatment completion or requires a treatment break of \geq than 5 days.
- d) No more than 20% of patients experience an acute toxicity, as defined below.

Acute toxicity is defined as any grade 3 or higher hematologic or non-hematologic toxicity, including skin changes, as graded by the NCI CTC Version 5.0, observed **within 30 days from the end of radiotherapy**, which is probably or definitely related to proton therapy.

Secondary Endpoints

Late toxicity is defined as any grade 3 or higher hematologic or non-hematologic toxicity which occurs more than 30 days after end of therapy. Late toxicities will be graded according to the CTC Version 5.0. Special attention will be paid to fibrosis and cosmesis. The time frame for late toxicity is open-ended because late toxicities have been known to occur a year or more after therapy. Follow-up for late toxicity will cease when a patient experiences disease progression since 2nd line therapies may then be initiated.

Cosmesis will be scored using the Harvard scoring system (scale = excellent, good, fair, poor) and CTC Version 5.0. In addition, cosmesis will be scored by the cosmesis and breast pain subscales of the Breast Cancer Treatment Outcomes Scale (BCTOS) instrument.

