Patients who experience acute toxicity	2	2	3	4
Posterior Prob [acute toxicity rate $> 20\%$]	0.80	0.62	0.70	0.76
Action	Terminate enrollment			

7.1.5 Statistical Analyses.

Feasibility: The posterior probability that this feasibility rate is 90% will be calculated. The feasibility rate and exact 90% CI will also be computed. The reasons why patients were not feasible will be tabulated.

Acute toxicity: All toxicities observed within 30 days from end of therapy will be graded by CTC Version 5.0 and tabulated. The posterior probability that this acute toxicity rate is 20% will be calculated.

Late toxicity: All toxicities observed later than 30 days from end of therapy will be graded by the CTC Version 5.0 and tabulated.

Cosmesis will be scored using the Harvard scoring system and CTC Version 5.0. BCTOS will be scored every 6 months and fold changes over time will be described and plotted.

Clinical efficacy: Local control (time to local failure) and overall survival will be estimated by the Kaplan-Meier method. It is likely that these time-to-event outcomes will be summarized after completion of the phase II study.

Estimation of Event Rates: The table below displays the 90% exact binomial confidence intervals based on 12 patients treated.

No. of Events	%	90% exact CI	No. of Events	%	90% exact CI
0	0.0	17.5*	7	58.3	31.5 , 81.9
1	8.3	.43 , 33.9	8	66.7	39.1 , 87.7
2	16.7	3.0 , 43.8	9	75.0	47.2 , 92.8
3	25.0	7.2 , 52.7	10	83.3	56.1 , 97.0
4	33.3	12.3 , 60.9	11	91.7	66.1 , 99.6
5	41.7	18.1 , 68.5	12	100.0	82.5*
6	50.0	24.5 , 75.5			* 90% 1-sided CI

7.2 PHASE II STUDY.

7.2.1 Design and Objectives.

Once feasibility and safety are established, then the phase II portion of the study will commence. A total of 57 patients will be enrolled; 12 patients are included from the feasibility study and 45 additional patients are enrolled in the phase II study. The two primary objectives are: to determine whether the rate of Grade 3+ acute toxicity is $\leq 20\%$ and whether the rate of maintained excellent to good cosmesis is $\geq 85\%$ at 2 years post-XRT. Only patients with excellent or good cosmesis at baseline contribute to this analysis.

7.2.2 Endpoints.

Acute Toxicity, as defined in Section 7.1.3

Cosmesis, as scored by the Harvard scale, CTC Version 5.0 and BCTOS scoring systems.

Late Toxicity, Local control and overall survival, as defined in Section 7.1.3

7.2.3 Rules for Early Termination for Acute Toxicity.

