A primary objective is to assess the rate of acute toxicity which will be tested by chi-square test at the end of the phase II study. But since accelerated partial breast radiotherapy with photons is a novel intensive treatment course, we have decided to continue Bayesian monitoring of acute toxicity throughout the course of the phase II study. Assuming a beta (1,5) prior, if the number of patients with Grade 3 or higher acute toxicity is greater than or equal to the number in the table below, then termination will be considered, because it is likely that the toxicity rate is $>20\%$, as noted by the Bayesian posterior probabilities.

Bayesian Rule for Acute Toxicity including skin changes				
Patients treated	20	30	40	50
Patients who experience acute toxicity	6	8	10	12
Posterior Prob [acute toxicity rate $>20\%$]	0.89	0.85	0.82	0.79
Action	Terminate enrollment			

CONFIDENTIAL

This material is the property of the University of Pennsylvania. Do not disclose or use except as authorized in writing by the study sponsor

7.2.4 Statistical Analyses.

The following are standard methods for data analysis which will be employed. Graphical analyses will include scatter plots, box plots, mean (\pm SE) plots and histograms. The distribution of continuous variables will be characterized with mean, median, standard deviation and range, while the distribution of categorical variables will be described with frequency, percentage and 95% CI. Toxicities will be categorized as acute or late and will be graded and tabled by toxicity type. The Grade 3+ acute toxicity rate and confidence interval will be calculated and a one sample chi-square test will be performed. The rate of excellent to good cosmesis at 2 years post-XRT and confidence interval will be calculated and a one sample chi-square test will be performed. Time to local failure and overall survival will be estimated by the Kaplan-Meier method.

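### Late toxicity is only tabulated, so any percentage reported is a crude proportion over unequal follow-up with no time horizon

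*Combined protocol and SAP*

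**What the plan says.** Section 2.2 makes late toxicity a secondary objective: "The secondary objectives of this study are to assess the late toxicities, cosmesis, and clinical efficacy". Section 7.1.3 defines it as Grade 3 or higher toxicity arising more than 30 days after therapy and sets no end to the window: "The time frame for late toxicity is open-ended because late toxicities have been known to occur a year or more after therapy". Observation can nevertheless be cut short: "Follow-up for late toxicity will cease when a patient experiences disease progression since 2nd line therapies may then be initiated".

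The planned analysis is descriptive. Section 7.1.5 (feasibility) says "All toxicities observed later than 30 days from end of therapy will be graded by the CTC Version 5.0 and tabulated". Section 7.2.4 (phase II) says "Toxicities will be categorized as acute or late and will be graded and tabled by toxicity type", with a general rule that "the distribution of categorical variables will be described with frequency, percentage and 95% CI". A method that handles censoring is planned only for two other outcomes: "Time to local failure and overall survival will be estimated by the Kaplan-Meier method".

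On numbers, section 7.2.1 states "A total of 57 patients will be enrolled; 12 patients are included from the feasibility study". Section 7.4 expects 2 patients a month, about 2.5 years of enrolment and about 4.5 years in total, the total being set by 2-year cosmesis. The Study Summary gives 8 years, and section 3.3 gives 10-12 patients a year. Sections 6.4 and 6.5 schedule toxicity assessments every 6 months to 5 years.

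**The concern.** The other main clinical outcomes have either a fixed window or a censoring-aware method. Acute toxicity has 30 days, the cosmesis test has 2 years with a rule for losses (section 7.3), and local failure and survival have Kaplan-Meier estimates. Late toxicity has neither, although the plan itself says such events can take a year or more to appear.

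A crude percentage therefore mixes patients followed for different lengths of time, and its value depends on when the data are cut. It cannot be set beside a 2-year or 5-year rate from another series. At stake is whether a named safety objective yields an interpretable number.

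**Working it through.** **1. The plan's own timeline.** The documents state no rate, horizon or precision for late toxicity; the figure that can be checked is the duration. 57 / 2 per month = 28.5 months = 2.38 years of accrual; adding 2 years gives 4.38 years. Section 7.4 says about 2.5 and 4.5, which agrees after rounding. With 57 evenly spaced entries at 24 a year and a cut at 4.5 years, follow-up runs from 2.15 to 4.48 years, so no patient reaches the scheduled 5 years.

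**2. Assumptions, none given in the documents.** The 5-year risk of Grade 3+ late toxicity is 10%, with either a constant hazard or a rising one (Weibull, shape 2). Progression plus loss by 5 years is 0%, or 14.5% (5% progression, 10% loss: 1 - 0.95 x 0.90), or 19.3% (5% and 15%: 1 - 0.95 x 0.85). The two non-zero values bracket what section 7.3 implies: 4 of 54 patients lost or progressed by 2 years gives 1 - (50/54)^2.5 = 17.5% by 5 years at a constant rate.

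**3. One case by hand** (constant hazard, no losses, follow-up uniform on 2.0-4.5 years).
- h = -ln(0.9)/5 = 0.02107 per year
- 2-year risk = 1 - exp(-2h) = 4.1%
- Expected crude proportion = 1 - [exp(-2h) - exp(-4.5h)] / (2.5h) = 1 - (0.9587 - 0.9095)/0.0527 = 6.6%

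Using the 57 discrete entries of step 1 gives 6.7%.

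**4. All cases.** The expected crude proportion is the mean over patients of the probability that a late event occurs before progression, loss or the data cut, with follow-up capped at 5 years.

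| Data cut | Follow-up, years | Constant hazard: no loss / with loss | Rising hazard: no loss / with loss | Shortfall against 10% |
|---|---|---|---|---|
| 4.5 years, 2 a month | 2.15 to 4.48 | 6.7% / 6.3-6.4% | 4.7% / 4.2-4.4% | 33-58% |
| 8 years, 10-12 a year | 2.35-3.29 up to 5 | 8.8-9.4% / 8.0-8.7% | 8.0-8.9% / 7.0-8.1% | 6-30% |
| All reach 5 years | 5 | 10.0% / 9.0-9.3% | 10.0% / 8.7-9.0% | 0% without loss, 7-13% with loss |

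Relative shortfalls are nearly the same at true 5-year risks of 5% and 20%. Under the rising hazard the 2-year risk is 1 - 0.9^((2/5)^2) = 1.7%, so at the 4.5-year cut the crude figure again lies between the 2-year and 5-year risks.

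**5. What drives it.** At the 4.5-year cut, staggered entry alone takes 10% to 6.7% (constant hazard). With everyone at 5 years, 10% loss alone gives 0.5 x (1 - 0.9 x 0.9) = 9.5%. For 5% progression alone, the progression hazard is -ln(0.95)/5 = 0.01026, and 0.02107/(0.02107 + 0.01026) x (1 - 0.9 x 0.95) = 9.75%. Progression contributes least under these splits. If it is treated as a competing event, that last reduction is part of the estimand and not a bias.

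**The case against.** The best defence is that a table by type and grade is a reasonable description of a secondary, untested and probably sparse endpoint in 57 patients. The late-toxicity text names no denominator and does not present a percentage as a 5-year risk; the percentage comes from the general rule on categorical variables. Precision is also poor: 6.6% and 10% of 57 are 3.8 and 5.7 expected events, and the exact 95% interval for 4/57 (1.9-17.0%) covers both rates. Late cosmesis already has a fixed 2-year horizon. All of this stands, and it keeps the point small. It does not supply a horizon.

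A reader might infer that the crude rate simply understates late risk, by about a third. The documents do not support that. They set no horizon, and against the 2-year risk the crude figure is too high. The one-third figure depends on the 4.5-year cut, which section 7.4 ties to cosmesis and not to late toxicity. Accrual at 2 a month plus 5 years of visits ends at about 2.4 + 5 = 7.4 years, inside the 8 years of the Study Summary, and the shortfall is then 0-13%.

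Nor does the stop at progression do much: section 7.3 expects only 4 patients lost or progressed before 2 years without already having failed on cosmesis. A crude rate diluted by recently entered patients is likewise not a concern here, since accrual will have closed by the 2-year cosmesis analysis.

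**Conclusion.** The point holds as a minor improvement. Late toxicity has an open-ended window, unequal follow-up and no method beyond tabulation, so a reported percentage would have no time attached. Its distance from the 5-year risk ranges from nil, if everyone completes 5 years without loss, to about 33-58% at a 4.5-year cut. The 8-year timeline with slower accrual lies between, at about 6-30%. These sizes rest on an assumed 10% 5-year risk, two assumed hazard shapes and assumed losses; only the timelines and the 4 early losses or progressions come from the documents. The defect is the missing horizon, not a bias in a fixed direction. Staggered entry and losses matter more than the stop at progression. Neither phase II primary test is affected.

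**What to change.** Keep the table by type and grade. Add to sections 7.1.5 and 7.2.4 the cumulative incidence of first Grade 3+ late toxicity, timed from the end of radiotherapy, at 2 years, and at 5 years once follow-up allows. Report 95% confidence intervals and numbers at risk, treat progression and death as competing events, and censor at the last toxicity assessment.

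The cost is a few sentences and a little more analysis, with no extra patients or visits. Intervals will be wide with 57 patients. Onset may be known only to about the nearest 6-monthly visit, with the plus or minus 2-month window of section 6.5. It should not be assumed that every date needed is already collected. Section 8.2 asks for start and stop dates of adverse events, but section 8.3.1 ends study treatment follow-up for adverse events 30 days after the last treatment, while section 7.1.3 leaves the late-toxicity window open. Those two sections must be reconciled so that late-event dates are captured.

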6.2 Pre-treatment

- Patient reported health-related quality of life will be assessed using the Breast Cancer Treatment Outcomes Scale (BCTOS) (See Appendix for Scale)
- Physician reported Harvard cosmetic assessment (Excellent, Good, Fair, Poor)

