We are interested in your evaluation of your physical appearance and functioning since your breast surgery. Please rate the following items on this four-point scale, according to your evaluation at this point in time. (Note: If you have had bilateral surgery, complete the items with regard to the difference between the right and left side.)

- 1 = no difference between treated and untreated breast and area
- 2 = slight difference between treated and untreated breast and area
- 3 = moderate difference between treated and untreated breast and area
- 4 = large difference between treated and untreated breast and area

 1. Breast size 2. Breast texture (hardening) 3. Arm heaviness 4. Nipple appearance 5. Shoulder movement 6. Arm movement 7. Breast pain 8. Ability to lift objects 9. Fit of shirt sleeve 10. Breast tenderness 11. Shoulder stiffness	
 12. Breast shape 13. Breast elevation (how high the breast is) 14. Scar tissue 15. Shoulder pain 16. Arm pain 17. Arm swelling 18. Breast swelling 19. Arm stiffness 20. Fit of bra 21. Breast sensitivity 22. Fit of clothing
--	---

CONFIDENTIAL

This material is the property of the University of Pennsylvania. Do not disclose or use except as authorized in writing by the study sponsor

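### BCTOS change is to be shown as a fold change, but on a scale coded 1 to 4 a ratio to baseline depends on the baseline score and on an arbitrary coding

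*Combined protocol and SAP*

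**What the plan says.** The only analysis sentence specific to BCTOS is under Cosmesis in section 7.1.5 (Statistical Analyses of the feasibility study): "BCTOS will be scored every 6 months and fold changes over time will be described and plotted". It does not state the denominator of the fold change or how values are pooled across patients.

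The form in section 15 (Attachments) has 22 items. It instructs the patient: "Please rate the following items on this four-point scale, according to your evaluation at this point in time". The lowest code reads "1 = no difference between treated and untreated breast and area" and the highest "4 = large difference between treated and untreated breast and area". Higher is worse, and the state without any deficit is coded 1. The form neither assigns items to subscales nor gives a scoring rule.

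Section 7.1.3 places BCTOS under the secondary endpoints: "In addition, cosmesis will be scored by the cosmesis and breast pain subscales of the Breast Cancer Treatment Outcomes Scale (BCTOS) instrument". Section 7.2.2 lists it again for phase II: "Cosmesis, as scored by the Harvard scale, CTC Version 5.0 and BCTOS scoring systems". Sections 6.2 and 6.4 collect it before treatment, at about one month, and then about every 6 months for 5 years. Section 7.2.4 lists general graphs and summaries for phase II and does not mention BCTOS.

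**The concern.** A fold change is interpretable when zero means none of the quantity, so that twice the score means twice as much. Here the lowest possible score is 1 by convention, and a score of 2 is not twice the deficit of a score of 1. The ratio combines how far the patient moved with where she started.

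Baselines are likely to differ. Every patient has had breast-conserving surgery, and the form asks about appearance and function since that surgery, so some pre-treatment scores may already carry a surgical deficit.

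What is at stake is the description of the only patient-reported instrument in the schedule. There is no control arm, so a reader would take the plotted course at face value, while part of its height would reflect the baseline mix.

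**Working it through.** **Inputs.** Item codes 1, 2, 3, 4 (section 15). Fold change over time as the summary (7.1.5). Pre-treatment score collected (6.2). Assumptions: the denominator is the pre-treatment score, and a subscale score is an item mean between 1 and 4. If it were a sum of k items, k would cancel and the ratio would be the same. The plan states no BCTOS figure, so there is none to reproduce. All scores below are illustrative.

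**Formula.** With baseline b, follow-up f and difference D = f − b, the fold change is F = f/b = 1 + D/b. For a fixed D, the excess over 1 is inversely proportional to b.

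**One-step worsening of an item (D = 1).**
- From 1 to 2: 2/1 = 2.00
- From 2 to 3: 3/2 = 1.50
- From 3 to 4: 4/3 = 1.33

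**Subscale worsening of 0.5.**
- b = 1.0: 1.5/1.0 = 1.50
- b = 2.0: 2.5/2.0 = 1.25
- b = 3.0: 3.5/3.0 = 1.17

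**Largest fold change attainable, 4/b.** 4.00 from b = 1, 2.00 from b = 2, 1.33 from b = 3. A patient who goes from 3 to the worst possible score plots at the same height as one who goes from 1.00 to 1.33.

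**Dependence on the coding.** Subtract 1 from every code, giving 0 to 3. The first step becomes 1/0, which is undefined. The second becomes 2/1 = 2.00 instead of 1.50, and the third 3/2 = 1.50 instead of 1.33. The differences stay at 1 throughout.

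**Pooling.** Suppose every patient worsens by exactly 0.5.
- All start at 1.0: mean fold change 1.50
- Half start at 1.0 and half at 2.0: (1.50 + 1.25)/2 = 1.375
- All start at 2.0: mean fold change 1.25

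The mean difference is 0.5 in all three cases. So if the baseline mix of patients still attending shifts over 5 years, the fold-change curve moves although no patient's change from baseline differs.

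**Asymmetry.** One patient goes from 1 to 2 and another from 2 to 1. The mean fold change is (2.00 + 0.50)/2 = 1.25, while the mean difference is 0. A geometric mean, √(2.00 × 0.50) = 1.00, removes the asymmetry but not the dependence on baseline or coding.

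**Reach.** The two powered tests in section 7.3 take no BCTOS input. With power = Φ{[|p0 − p1| − 1.2816√(p0(1 − p0)/n)] / √(p1(1 − p1)/n)}:
- Acute toxicity, n = 57, 35% against 20%: (0.15 − 0.0810)/0.0530 = 1.303, power 90.4%
- Harvard cosmesis, n = 50, 70% against 85%: (0.15 − 0.0831)/0.0505 = 1.326, power 90.8%

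Both agree with the stated 90%. The Bayesian termination rules in 7.1.4 and 7.2.3 use feasibility and acute toxicity only.

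**The case against.** The best defence is that nothing is decided on this measure. The sentence promises description and plots. No BCTOS hypothesis, threshold or stopping boundary exists. All of that stands, and it sets the size of the point. A reader might infer that the trial's cosmesis conclusion is at risk; the documents do not support this, because the powered test is on the physician-rated Harvard scale.

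Second, the sentence belongs to the 12-patient feasibility study, and the general methods in 7.2.4 (box plots, mean plots, means and medians) could show BCTOS on its original scale. So one cannot say that ratios are all the reader will see. But 7.2.4 neither names BCTOS nor withdraws the fold-change sentence, and 7.1.5 remains the only BCTOS-specific method.

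Third, within one patient the ratio to a fixed baseline preserves the direction and order of change. Distortion arises only when patients with different baselines are pooled or compared. A reader might infer that the plan will overstate worsening in patients who start well relative to those who start badly, but no comparison by baseline score is planned. The baseline spread is not given either. Section 7.3 expects 3 of 57 patients to have fair cosmesis at entry, which hints that marked deficits may be few, though on a different, physician-rated scale.

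Fourth, one could argue that the items are ordinal, so differences are no better founded than ratios. Calling the three steps equal does assume equal spacing, so ordinality is not the ground for this point. The ground is the arbitrary origin, which affects ratios and leaves differences unchanged. The spacing question is a reason to show a category-shift summary as well.

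**Conclusion.** The point holds as a minor one about presentation. The fold change is a poor summary for an instrument coded 1 to 4: the same one-step worsening reads as 2.00-, 1.50- or 1.33-fold according to baseline, and pooled values depend on the baseline mix and the coding. This rests on the pre-treatment score being the denominator and on subscale scores being item means or sums; the documents state neither. The size of the distortion in this trial cannot be computed, because the spread of baseline scores is not given. Sample size, significance level, powered tests and termination rules are unaffected.

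**What to change.** In section 7.1.5, replace fold change with the difference from the pre-treatment score for the cosmesis and breast-pain subscales, at month 1 and at each 6-month visit, as mean or median change with a 95% CI. Show it with the observed scores by visit, the number of patients contributing, and a category-shift summary from pre-treatment. Carry the same text into 7.2.4, since BCTOS is again an endpoint in phase II. State which items form each subscale and how it is scored, because any change analysis needs this.

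No responder cut-off should be added unless the sponsor chooses and justifies one; the documents give no threshold for meaningful change. The cost is a few sentences. The required scores are already in the schedule, and no change to sample size or significance level follows.

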Clinical Efficacy. Time to local failure will be defined as the time from the start of radiation therapy to local failure. Overall survival will be defined from the time from the start of radiation therapy to death due to any cause or last patient follow-up. These outcomes will likely be summarized during the phase II study.

7.1.4 Rules for Early Termination for Feasibility and Acute Toxicity.

Bayesian probability calculations will be employed to define rules of early termination for feasibility and safety. The tables below indicate termination rules after groups of 3 patients have been treated, although the Bayesian probability of an event may be calculated at any time during the trial. Hundreds of patients

with certain types of cancer have undergone radiation therapy with protons. Thus, we will assume a modest amount of “prior” feasibility and safety data for proton for our Bayesian calculations.

Feasibility

We will assume a beta (5,1) prior, which is information equivalent to feasibility established in 5 of 6 treated patients. A feasibility rate $\geq 90\%$ is considered acceptable. If the number of patients in whom proton is deemed feasible is less than or equal to the number in the table below then termination will be considered as it is highly unlikely that the feasibility rate is $> 90\%$, as noted by the Bayesian posterior probabilities.

Bayesian Rule for Feasibility				
Patients treated	3	6	9	12
Patients in whom proton is feasible	1	4	6	9
Posterior Prob[feasibility rate $> 90\%$]	0.04	0.09	0.04	0.08
Action	Terminate enrollment			

Acute Toxicity

Acute toxicity with accelerated partial breast radiotherapy with photons is quite low, although skin toxicity is fairly common. Proton therapy is expected to spare normal tissues; therefore, a rate of Grade 3 or higher acute toxicity observed **within 30 days from the end of radiotherapy**, including skin changes, which is probably or definitely related to proton therapy of $\leq 20\%$ is considered acceptable. We will assume a beta (1,5) prior, which is information equivalent to Grade 3 or higher acute toxicity in one of 6 treated patients. If the number of patients with Grade 3 or higher acute toxicity is greater than or equal to the number in the table below, then termination will be considered, because it is likely that the toxicity rate is $> 20\%$, as noted by the Bayesian posterior probabilities.

Bayesian Rule for Acute Toxicity including skin changes				
Patients treated	3	6	9	12

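### The phase II acute toxicity stopping table (7.2.3) prints posterior probabilities that its stated beta(1,5) prior does not give: 0.89, 0.85, 0.82, 0.79 should read 0.78, 0.75, 0.72, 0.70

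*Combined protocol and SAP*

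**What the plan says.** Two sections give a Bayesian rule for Grade 3 or higher acute toxicity against a 20% limit.

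- **Section 7.1.4 (feasibility, 12 patients)** uses a beta(1,5) prior, described as "information equivalent to Grade 3 or higher acute toxicity in one of 6 treated patients". At 2/3, 2/6, 3/9 and 4/12 the table prints posterior probabilities of "0.80 0.62 0.70 0.76". The introduction to that section adds that tables are given for groups of three patients, "although the Bayesian probability of an event may be calculated at any time during the trial".
- **Section 7.2.3 (phase II)** continues the monitoring and names the same prior: "Assuming a beta (1,5) prior, if the number of patients with Grade 3 or higher acute toxicity is greater than or equal to" the tabulated number, termination will be considered. The looks are "Patients treated 20 30 40 50", the stopping counts are "Patients who experience acute toxicity 6 8 10 12", and the posterior row is "0.89 0.85 0.82 0.79". The reason given for stopping is that these posterior probabilities make a rate above 20% likely.

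No other prior is stated for toxicity monitoring in phase II. Section 8.4 refers to section 7.2 for the stopping rules.

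**The concern.** The prior, the counts and the sample sizes together fix the posterior probability, so the row in 7.2.3 can be checked directly. It does not follow from the prior named in the sentence above it.

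Acute toxicity is a primary endpoint, and reaching a count means only that termination is considered. The printed probability is therefore the protocol's own statement of how strong the evidence is at that point. If beta(1,5) is intended, that strength is overstated at every look. If the row is what was intended, the prior sentence is wrong, and the plan has moved without explanation from an informative prior in 7.1.4 to a much less favourable one. Anyone recalculating the probability between looks would get a different answer depending on which half of 7.2.3 they followed.

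**Working it through.** **Inputs.** From 7.2.3: prior beta(1,5); (x, n) = (6, 20), (8, 30), (10, 40), (12, 50); limit 0.20. From 7.1.4: prior beta(1,5); (x, n) = (2, 3), (2, 6), (3, 9), (4, 12); same limit.

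**Formula.** With a beta(a, b) prior and x events in n patients, the posterior is Beta(a + x, b + n − x), and the tabulated quantity is P(rate > 0.20) = 1 − F(0.20), where F is the distribution function of that posterior. When a = 1 this equals P(Bin(n + b, 0.20) ≤ x), which was used as a cross-check and agreed.

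**Step 1: confirm that this is the protocol's method, using the 7.1.4 tables.**

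| x/n | Posterior | Computed, beta(1,5) | Printed | Computed, beta(1,1) |
|---|---|---|---|---|
| 2/3 | Beta(3,6) | 0.797 | 0.80 | 0.973 |
| 2/6 | Beta(3,9) | 0.617 | 0.62 | 0.852 |
| 3/9 | Beta(4,11) | 0.698 | 0.70 | 0.879 |
| 4/12 | Beta(5,13) | 0.758 | 0.76 | 0.901 |

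The 7.1.4 feasibility table is also reproduced with its stated beta(5,1) prior and 90% limit: 0.038, 0.090, 0.044 and 0.083 against the printed 0.04, 0.09, 0.04 and 0.08. The formula is the one the authors used, and both 7.1.4 tables are right.

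**Step 2: apply it to 7.2.3.**

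| x/n | Posterior, beta(1,5) | Computed, beta(1,5) | Printed | Printed − computed | Computed, beta(1,1) |
|---|---|---|---|---|---|
| 6/20 | Beta(7,19) | 0.7800 | 0.89 | 0.110 | 0.8915 |
| 8/30 | Beta(9,27) | 0.7450 | 0.85 | 0.105 | 0.8492 |
| 10/40 | Beta(11,35) | 0.7205 | 0.82 | 0.0995 | 0.8177 |
| 12/50 | Beta(13,43) | 0.7021 | 0.79 | 0.088 | 0.7933 |

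No cell agrees under beta(1,5). The 8/30 value is 0.74501 before rounding, hence 0.75. All four cells agree under beta(1,1).

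**Step 3: look for another explanation.**

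- Over all integer priors with a and b from 1 to 20, only (1,1) reproduces the 7.2.3 row to two decimals, and only (1,5) reproduces the 7.1.4 toxicity row. The two tables share no integer prior.
- Counts one higher (7, 9, 11, 13) under beta(1,5) give 0.89, 0.85, 0.83 and 0.80, which match only the first two cells.
- Lowering n by the 12 feasibility patients gives 0.93 to 0.99; raising it by 12 gives 0.37 to 0.40.
- The plain binomial P(Bin(n, 0.20) ≤ x) gives 0.91, 0.87, 0.84 and 0.81.
- Some non-integer priors also fit, for example beta(0.9, 0.6), so beta(1,1) is the likely source and not a proven one.

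**Step 4: how far apart the two priors are.** Before any data, P(rate > 0.20) is 1 − (1 − 0.8⁵) = 0.8⁵ = 0.328 under beta(1,5), and 0.80 under beta(1,1). For a recalculation between looks, 7 events in 25 patients gives 0.76 under beta(1,5) and 0.87 under beta(1,1).

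**Step 5: are the counts affected?** With one event fewer at each look (5, 7, 9, 11), beta(1,5) gives 0.617, 0.599, 0.588 and 0.580. A single cutoff above 0.617 and no higher than 0.702 would therefore produce exactly 6, 8, 10 and 12. Under beta(1,1) one event fewer gives 0.769, 0.730, 0.704 and 0.685, so a cutoff above 0.769 and no higher than 0.793 produces the same counts.

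**The case against.** The best case against giving this much weight is that the rule operates through the counts. Section 7.2.3 triggers on the number of events, states no numeric posterior cutoff, and says only that termination will be considered. The counts are coherent under either prior (step 5). At 0.70 to 0.78 it is still fair to call a rate above 20% likely, and those values lie within the 0.62 to 0.80 span of the 7.1.4 table. Sample size, power and the final chi-square test do not use the prior. The remark about calculating at any time stands in 7.1.4, is not repeated in 7.2.3, and has no action attached to it. No section says who reads the posterior row, so its influence on the data and safety monitoring committee is an inference.

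All of that stands and limits the consequences. It does not remove the error: nothing elsewhere in the documents reconciles the prior with the row, and the row is what the text offers as the reason to stop. The objection also rightly notes that arithmetic alone cannot say which element was intended, or that the counts were intended as printed.

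**Conclusion.** The concern holds. The prior and the posterior probabilities in 7.2.3 contradict each other in all four cells. If beta(1,5) is intended, the printed values are too high by 11, 10.5, 10 and 9 percentage points at 20, 30, 40 and 50 patients. If beta(1,1) is intended, the prior sentence is wrong and the departure from 7.1.4 is unexplained.

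The size rests only on the beta-binomial calculation that reproduces both 7.1.4 tables. That beta(1,1) was the actual source is inferred from the numerical match. The counts are not shown to be wrong, and with them unchanged no decision at the four tabulated looks differs. It should still be corrected, because it concerns the stated justification of a safety stopping rule on a primary endpoint.

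**What to change.** Reconcile the prior sentence and the probability row in 7.2.3, with the sponsor confirming that 6, 8, 10 and 12 are the intended counts. There are two ways:

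- **(a)** Keep beta(1,5), as in 7.1.4, and reprint the row as 0.78, 0.75, 0.72, 0.70.
- **(b)** Keep the printed row, state that phase II monitoring uses beta(1,1), and explain why it differs from 7.1.4. The explanation should address the fact that this prior starts at a probability of 0.80 for a rate above 20% before any patient is treated, slightly above the 0.79 printed for stopping at 12/50. It should also say why the prior information assumed in 7.1.4 is set aside.

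The section should also say that any calculation between looks uses the same prior. The cost is one table row, or one sentence with a short justification, by protocol amendment. Neither option changes a boundary count, the sample size or data collection.
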